### 6.3. Enrollment Design

The study is planned to include up to 448 subjects.

This study will be conducted in up to 30 centers, located in the United States (U.S.), Canada and European Union (EU). The study will be registered and results will be reported to the U.S. database maintained by the United States National Institutes of Health (NIH) on the United States National Library of Medicine's ("NLM") website [www.clinicaltrials.gov](http://www.clinicaltrials.gov) under Title VIII of the Food and Drug Administration Act of 2007 ("FDAAA"). The expected duration of subject enrollment is approximately 90 days ( $\pm$  15 days). Subjects will be followed through 90 days ( $\pm$  15 days) with assessments at hospital discharge and 90 days ( $\pm$  15 days).

An independent Core Lab will confirm occlusion as recorded on baseline CTA/MRA imaging, and score reperfusion. In addition, the independent Core Lab will assess 24 hours (-8/+12 hours) post treatment images for evidence of ICH. An independent CEC will adjudicate study safety endpoints. An independent DMC will evaluate all adverse events throughout the study and will monitor subject safety. The CEC and DMC will perform their duties in accordance with

this protocol, the DMC Charter, and the CEC Charter associated with this study.

#### **6.4. Site Selection**

The sponsor or a representative of the sponsor will assess each potential site to ensure the Investigator and their staff has the facilities and expertise required for the study. Sites will be selected based upon a site qualification assessment considering appropriate facilities, and the qualifications of the Investigator(s). Individual Investigators will be evaluated by the sponsor based on experience with the intended procedure(s), and ability to conduct the study according to the study protocol.

Investigators and sites will be selected based upon the following factors:

- Previous experience with clinical research and mechanical thrombectomy procedures.
- Experience in conducting randomized, controlled clinical studies.
- Willingness to observe confidentiality at all times.
- Currently treating subjects who meet the inclusion/exclusion criteria.
- Ability to enroll an adequate number of subjects.
- Ability to perform required clinical testing, including angiography, CT, and/or MRI.
- Ability and willingness to provide the sponsor's representatives, FDA and local regulatory authorities access to the hospital records, study files, and subject files as they pertain to the study.
- Willingness to participate, including compliance with all aspects of the study.
- Adequate staffing to conduct the study. This includes:
  - Principal Investigator (PI): Responsible for overall clinical management of subjects enrolled at his/her institution. Assumes overall responsibility and accountability for the clinical team and for data obtained from each subject participating in the study. Ensures compliance with the protocol, applicable laws, and applicable regulations; ensures informed consents are signed, and reviews and signs eCRFs indicating documents are accurate and complete.
  - Sub/Co-Investigator(s) (Sub-I/Co-I): Responsible for study activities in coordination with PI and in accordance with the investigational plan. Assume the responsibility of the PI should the PI resign from the study. A site is not required to have a co-investigator.
  - Study Coordinator: Assists PI with study activities as delegated by the PI, including tracking subjects involved in the study, scheduling testing and follow-up visits, maintaining study records, completing eCRFs to the sponsor in a timely manner.
  - Blinded and Certified Assessor: Responsible for clinical evaluations at 90-day follow-up

## 6.5. Inclusion Criteria

Study subjects must meet ALL of the inclusion criteria listed below:

- 1) Clinical signs consistent with acute ischemic stroke
- 2) Pre-stroke Modified Rankin Score  $\leq 2$
- 3) Age 18 years and no upper limit (patient must be 18 years old at time of consent.)
- 4) NIHSS  $\geq 6$  at the time of randomization
- 5) Subject is able to start treatment (defined as time of arterial puncture) within 24 hours of stroke onset or last known well and within 90 minutes from last baseline CT/ MRI.
- 6) Imaging: For strokes in the anterior circulation the following imaging criteria should also be met:
  - a) If stroke onset (as defined by the time the patient was last seen at baseline) is within 6 hours: Baseline ASPECTS  $\geq 6$  on non-contrast CT (NCCT) or DWI-MRI;
  - b) If stroke onset is within 6-24 hours, advanced imaging with either CT perfusion or DWI-MRI is required. Baseline infarct volume must be  $\leq 50$ cc for patients under 80 years old and  $\leq 20$ cc for patients 80 years or older.
- 7) Location: Angiographic confirmation of an occlusion of an ICA (including T or L occlusions), M1 or M2 MCA with eTICI flow of zero (0) – one (1).
- 8) Patients for whom IV t-PA is indicated, are treated with IV t-PA without delay.
- 9) IV t-PA, if used, is initiated within three (3) hours of stroke onset (onset time is defined as the last time when the patient was witnessed to be at baseline), with investigator verification that the subject has received/is receiving the correct IV t-PA dose for the estimated weight.
- 10) Consent: The patient or the patient's LAR has signed and dated an Informed Consent Form.
- 11) Will comply with protocol follow-up schedule.
- 12) Patient was ambulatory prior to stroke, i.e. able to walk without another person's assistance.

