Ischemic strokes can be due to large-vessel atherosclerosis, aorto-cardioembolism, small-vessel occlusion, other determined causes, and undetermined causes. Acute ischemic stroke due to large vessel occlusion (LVO)-vertebral, basilar, carotid terminus, middle and anterior cerebral arteries- likely portends a worse prognosis than stroke unassociated with LVO.

The large vessels of the brain include the Internal Carotid Artery (ICA), Middle Cerebral Artery (MCA), Anterior Cerebral Artery (ACA), Vertebral Artery (VA), and the Basilar Artery (BA). Occlusion of these large arteries in ischemic stroke is associated with significant disability and mortality. Revascularization of intracranial arterial occlusions is the therapeutic goal in stroke therapy. Endovascular mechanical revascularization (thrombectomy) is an increasingly used method for intracranial large vessel recanalization in acute stroke. Currently, a number of mechanical recanalization devices are in clinical use. First generation devices included the Merci Retriever device. Second generation devices based on stent-like technology, referred to as “Stentriever®,” “stent-retrievers,” “stent retrievers,” or simply “retrievers” are currently the standard of care for treatment of LVO and acute ischemic stroke in a defined subset of AIS patients.

The Envi™-SR has been developed and CE marked in Europe for revascularization in patients experiencing AIS. The Envi™-SR is approved for use in the US strictly within the confines of the NV-001 Study. In this study the Envi™-SR is intended for use in the neurovasculature per the indications listed below.

1. The Envi™-SR is indicated for use to restore blood flow in the neurovasculature by removing thrombus for the treatment of acute ischemic stroke to reduce disability in patients with a persistent, proximal anterior circulation, large vessel occlusion, and smaller core infarcts who have first received intravenous tissue plasminogen activator (IV t-PA).

Endovascular therapy with the device should be started within 6 hours of symptom onset.

2. The Envi™-SR is intended to restore blood flow in the neurovasculature by removing thrombus in patients experiencing ischemic stroke within 8 hours of symptom onset. Patients who are ineligible for IV t-PA or who fail IV t-PA therapy are candidates for treatment.

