3. The Envi™-SR is indicated for use to restore blood flow in the neurovasculature by removing thrombus for the treatment of acute ischemic stroke to reduce disability in patients with a persistent, proximal anterior circulation, large vessel occlusion of the internal carotid artery (ICA) or middle cerebral artery (MCA)-M1 segments with smaller core infarcts (0-50 cc for age < 80 years, 0-20 cc for age ≥ 80 years). Endovascular therapy with the device should start within 6-24 hours of time last seen well in patients who are ineligible for intravenous tissue plasminogen activator (IV t-PA) or who fail IV t-PA therapy.

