### **1.1.3. Ethical Considerations – Global**

The Envi™-SR device is not cleared in either the U.S. by the FDA or in Canada by Health Canada. It is an investigational device that may be used in the U.S. and Canada within the confines of the NV-001 Study. The purpose of this IDE Study is to gather information on device effectiveness, safety, and performance to support an application for clearance to FDA and Health Canada.

For subjects enrolled in European study sites, the Envi™-SR device will be used according to the investigational indications for use per the instructions for use. It is an investigational device that may be only used within the confines of the NV-001 Study. The collection and analysis of the data requires ethical approval.

The intent of the NV-001 Study is to collect data on subjects in a prospective manner; all subjects who are screened and meet all Inclusion/Exclusion criteria will be included in the analysis. Coded subject data in the form of angiographic and CT and/or MRI images, and completed case report forms are required in order to assess the study endpoints. Informed consent will be sought from the subjects or their legal representative for participation and to give permission for the sponsor and subcontractors (Contract Research Organization (CRO), Clinical Events Committee (CEC), Data Monitoring Committee (DMC), and Core Lab) to have access to these data.

Physicians should follow local practice guidance's, their own routine best practice, requirements per this protocol, and the Envi™-SR or control device's instructions for use, when participating in the study.

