### 6.2. Control Device

Currently there are two FDA-cleared stent retriever families with indications for treatment of acute ischemic stroke: the Stryker Neurovascular Trevo® family and the ev3 Neurovascular/Medtronic Solitaire™ family. The Trevo® family consists of the Trevo ProVue®

Retriever, Trevo® XP ProVue Retriever, and Trevo NXT™ ProVue Retriever. The Solitaire™ Revascularization Device family includes the following: Solitaire™ Platinum, Solitaire™ 2, Solitaire™ 4, and Solitaire™ X.

All Control Devices used must be used within their Indications for Use.

The proposed Envi™-SR indications for use match the Trevo® family of devices. Hence the time from stroke onset to usage (up to 24 hours) and imaging criteria are identical and the inclusion/exclusion criteria for the NV-001 study align with this indicated patient population.

The Solitaire™ Revascularization Device family has similar indications for use, however the indicated time from stroke onset to usage is up to 16 hours from onset or time last seen well (TLSW). Therefore, in the case of a subject randomized to the Control Device at 16 to 24 hours from onset or TLSW, only the Trevo® family will be permitted to be used.

The devices in Table 6.1 are currently cleared and may be used as the Control Device.

Table 6.1: Control Devices for ENVI RCT		
Family	Product	Size
Stryker Neurovascular Trevo®	Trevo ProVue® Retriever	4x20mm
	Trevo® XP ProVue Retriever	3x20mm
		4x20mm
		4x30mm
		6x25mm
ev3 Neurovascular/ Medtronic Solitaire™	Solitaire™ Platinum Revascularization Device	4x20mm
		4x40mm
		6x20mm
		6x24mm
		6x40mm
	Solitaire™ X Revascularization Device	4x20mm
		4x40mm
		6x20mm
		6x24mm
		6x40mm
	Solitaire™ 2 Revascularization Device	4x15mm
		4x20mm
		4x40mm
		6x20mm
		6x30mm

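### M2 occlusions are eligible up to 24 hours, but beyond 8 hours they fit none of the three indications sought, and for Control subjects at 16-24 hours the rules in Section 6.2 cannot all be met

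*Combined protocol and SAP*

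**What the plan says.** **Eligibility.** Criterion 5 in Section 6.5 requires that treatment can start "within 24 hours of stroke onset or last known well and within 90 minutes from last baseline CT/ MRI". Criterion 7 lists ICA, "M1 or M2 MCA with eTICI flow of zero" to one. Criterion 6b adds, for the late window, "If stroke onset is within 6-24 hours, advanced imaging with either CT perfusion or DWI-MRI is required", with core-volume limits by age. It sets no limit by vessel segment. Nothing in Section 6.6 excludes a late M2 occlusion. The synopsis repeats the same criteria.

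**Indications sought** (synopsis and Section 1). Indication 1 applies after IV t-PA and ends at 6 hours. Indication 2 covers treatment "in patients experiencing ischemic stroke within 8 hours of symptom onset" and names no vessel. Indication 3 runs from 6 to 24 hours and is confined to "large vessel occlusion of the internal carotid artery (ICA) or middle cerebral artery (MCA)-M1 segments with smaller core infarcts".

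**Device rules.** Section 6.2 states: "All Control Devices used must be used within their Indications for Use". It also says that the Envi-SR indications match those of the Trevo family, that the Solitaire indications are similar but stop at 16 hours, and that only Trevo may be used for Control at 16-24 hours. It concludes that "the inclusion/exclusion criteria for the NV-001 study align with this indicated patient population". Section 1.1.3 adds that at European sites the Envi-SR "device will be used according to the investigational indications for use per the instructions for use".

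**The concern.** Read together, these sections admit a group of subjects whom the indications leave out. Two things are at stake.

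The first is conduct. For some of these subjects a site cannot satisfy every rule in the protocol at once, so how their treatment is classified is left to judgement case by case.

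The second is inference. Late M2 subjects count in the pooled ITT comparison of 90-day mRS and of sICH, and that comparison is meant to support three indications that do not cover them. The analyses specified in Section 8.3 do not separate them out. The time-last-seen-well analysis in Section 8.3.7 splits at 6 hours and ignores occlusion site.

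**Working it through.** The plan gives no figure to reproduce. The check is a cross-tabulation of M2 by time from onset against the indications and the Control-device rules.

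| M2, time from onset | Indication that can apply | Control device under Section 6.2 |
|---|---|---|
| 0-6 h | 1 (after IV t-PA, if M2 counts as a proximal large vessel) or 2 (IV t-PA ineligible or failed) | No conflict shown |
| >6-8 h | 2 only | No conflict shown |
| >8-16 h | None | Trevo not covered if its indications match; Solitaire undetermined, because its vessel segments are not stated |
| >16-24 h | None | Only Trevo permitted; not covered if its indications match |

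ICA and M1 occlusions can still be covered to 24 hours by indication 3, subject to its IV t-PA and core-volume terms, so this gap is specific to M2. It spans 24 − 8 = 16 of the 24 eligible hours.

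In the last row, three statements in Section 6.2 collide: the Envi-SR indications match Trevo's, Control Devices must be used on-indication, and only Trevo may be used. If the first holds, Trevo does not cover M2 at that time, and the second and third cannot both be met.

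**Clock.** Indication 2 counts from symptom onset, whereas criterion 5 allows onset or last known well. A subject with unwitnessed onset could arguably fit indication 2 later than 8 hours from last known well. Criteria 6a and 9 define onset as the last time the patient was at baseline, which largely closes that route. Subjects with witnessed onset are unaffected by it.

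**Size.** All shares are assumptions, and occlusion site and time are taken as independent.

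Outside every indication = (M2 share) × (share beyond 8 h) × N, with M2 at 10-25% and 20-35% beyond 8 h:
- Low: 0.10 × 0.20 = 2.0%, so 5.4 of 270 and 9.0 of 448.
- High: 0.25 × 0.35 = 8.75%, so 23.6 of 270 and 39.2 of 448.

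Device conflict = (M2 share) × (share at 16-24 h) × Control N, with 5-15% at 16-24 h and 135 Control subjects:
- Low: 0.10 × 0.05 × 135 = 0.7.
- High: 0.25 × 0.15 × 135 = 5.1.

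**The case against.** The strongest reply is that Section 6.2 does name a device for 16-24 hours, without a limit by vessel, and that the Trevo and Solitaire labels are not in the documents. Whether Trevo is off-label for a late M2 occlusion rests on reading one summary sentence about matching indications segment by segment. That is fair as to the labels themselves. The protocol's own statements still cannot all be met.

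A reader might infer three stronger things, which the documents do not support:

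- *No permitted Control device from 8 hours on.* The conflict can be shown only beyond 16 hours. At 8-16 hours Solitaire may or may not be covered.
- *Automatic loss from the Per Protocol set.* A Control subject treated with Trevo or Solitaire has been treated as assigned, so the Section 10.1 item on not following the randomised assignment does not apply. Off-indication Control use is not on that list, although the list is open-ended. Section 5.1.3 removes only subjects whose major deviation materially alters the protocol's intent or outcome for them. Exclusion is possible, not certain.
- *More deviations in Control than in Envi-SR.* Section 1 ties in-study Envi-SR use to the three indications, Section 1.1.3 holds physicians to the instructions for use of either device, and Section 6.8.3 directs sites to them. Both arms are tied to labelling, and no difference between arms is shown.

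It is also true that including M2 looks deliberate. Section 2.1 describes use in ICA, M1 and M2, and M2 is a randomisation stratum. But that description gives no time window and is not one of the indications. Finally, Section 8.3.1 adjusts for the stratification factors and foresees subgroup analyses. These soften the analysis concern but do not specify an M2-by-time or indication-based subset. Section 8 defers detail to a separate SAP whose text was not available here, so its absence there cannot be asserted.

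**Conclusion.** The inconsistency is real and holds at any subject share. Beyond 8 hours from onset, eligible M2 subjects are outside every indication sought, so the alignment statement in Section 6.2 is not true for them. For M2 Control subjects at 16-24 hours, the three device statements in that section cannot all be met.

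The number affected is not known from the documents. Under the assumed shares it is about 2-9% of ITT outside all indications, and about 1-5 Control subjects in a trial of 270 in the demonstrable device conflict. ITT is the primary population and stays interpretable as a comparison of the devices in the subjects enrolled. What weakens is the link from that result to the indications it is meant to support.

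**What to change.** **Protocol.** Reconcile the three indications (synopsis and Section 1), inclusion criteria 5 and 7 (synopsis and Section 6.5), and the alignment, on-indication and 16-24 hour statements in Section 6.2. State how M2 stands for each Control family by time window. Which text moves is for the sponsor and its clinical leads.

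**SAP.** For each ITT subject, derive which indication applies (1, 2, 3 or none) from occlusion site, time from onset or last seen well, IV t-PA use and failure (as defined in Appendix A), core volume and age. Fix the clock used for indication 2 in advance. Report the count in each category by arm. Repeat the primary effectiveness and primary safety analyses, as sensitivity analyses, in subjects within at least one indication. Keep full ITT as primary.

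**Cost.** Protocol wording, one derived variable and two repeat analyses. Dropping 2.0-8.75% of subjects widens the intervals by a factor of 1/√0.98 = 1.01 to 1/√0.9125 = 1.05, so about 1-5%. Subjects outside the indications for other reasons would add to this. If eligibility is what changes, there would be a few percent fewer candidates under the same assumptions.

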## 6.6. Exclusion Criteria

Subjects must NOT meet ANY of the exclusion criteria listed below:

- 1) Life expectancy likely less than six (6) months.
- 2) Females who are pregnant or breastfeeding.
- 3) Known history of severe allergy (more than rash) to contrast medium that cannot be medically controlled.
- 4) Suspicion of renal failure (Renal failure as defined by a serum creatinine >3.0 mg/dL (264 µmol/L) or Glomerular Filtration Rate (eGFR) <30).
- 5) Severe, sustained hypertension (Systolic Blood Pressure >185 mmHg or Diastolic Blood Pressure >110 mmHg) NOTE: If the blood pressure can be successfully reduced and maintained at the acceptable level using medication the subject can be enrolled.
- 6) Currently participating in another interventional (drug, device, etc.) research project that may confound the results of this study.
- 7) Known hereditary or acquired hemorrhagic diathesis, coagulation factor deficiency. (A subject without history or suspicion of coagulopathy does not require INR or prothrombin time lab results to be available prior to enrollment.)
- 8) Known history of platelet count <100,000/µL.
- 9) Baseline blood glucose of <50mg/dL (2.78 mmol) or >400mg/dL (22.20 mmol).
- 10) Subjects with occlusions in multiple vascular territories (e.g., bilateral anterior circulation, or anterior/posterior circulation).
- 11) CT or MR evidence of hemorrhage.
- 12) Seizures at stroke onset.
- 13) Suspicion of aortic dissection.
- 14) Patients with known hypersensitivity to nickel-titanium.
- 15) Evidence of dissection in the extra or intracranial cerebral arteries.
- 16) Stenosis, or any occlusion, in a proximal vessel that requires treatment or prevents access to the site of occlusion.
- 17) Presumed septic embolus, suspicion of bacterial endocarditis, or other serious infection.
- 18) Suspected cerebral vasculitis based on medical history and CTA/Magnetic Resonance Angiogram (MRA).
- 19) Excessive vascular access tortuosity that will likely prevent endovascular access.
- 20) Baseline CT or Magnetic Resonance Imaging (MRI) showing intracranial tumor (except asymptomatic small meningiomas less than three (3) cm).
- 21) Significant mass effect with midline shift
- 22) Treatment with any cleared thrombectomy devices or other intra-arterial (neurovascular) therapies three months prior to use of treatment device
- 23) Unlikely to be available for 90-day ( $\pm$  15 days) follow-up (e.g. no fixed home address, visitor from overseas).
- 24) Rapid neurological improvement prior to study enrollment suggesting resolution of signs/symptoms of stroke such as a decrease that leads to a NIHSS below the study cut-off of six (6).
- 25) Patient has suffered a hemorrhagic or ischemic stroke or TIA within the last three (3) months.
- 26) Patients with a pre-existing neurological or psychiatric disease that would confound the neurological or functional evaluations, mRS score at baseline must be  $\leq$  2. This excludes patients who are severely demented, require constant assistance in a nursing home type setting or who live at home but are not fully independent in activities of daily living (toileting, dressing, eating, cooking and preparing meals, etc.).
- 27) Known cancer with metastases.
- 28) Subject currently uses or has a recent history of illicit drug(s), which includes marijuana.
- 29) Recent past history (within three (3) months) or clinical presentation of intracranial

hemorrhage (ICH), subarachnoid hemorrhage (SAH), ruptured arteriovenous malformation (AVM) or ruptured aneurysm.

30) The patient is in a coma.

